1.2.1. Option A

Hospitalized infants and children who are infected with RSV will be randomly assigned to a treatment regimen in this study, with 60 subjects planned per regimen. At least 120 subjects are planned to be enrolled up to a maximum of 180 subjects. An effort will be made to enroll at least 90 subjects aged between 28 days and 24 months and at least 12 subjects aged between 24 and 36 months. The number of subjects with comorbidities will be limited to 20%; additional comorbid subjects aged between 24 and 36 months may be allowed to enroll if the 20% threshold is reached before 12 subjects aged between 24 and 36 months are enrolled into the study.

Subjects will be randomized in a 1:1:1 ratio to Regimen A, B, or C:

- Regimen A (low-dose lumicitabine): a single 40 mg/kg LD (Dose 1) followed by nine 20 mg/kg MDs (Doses 2 to 10) of lumicitabine, administered twice daily.
- Regimen B (high-dose lumicitabine): a single 60 mg/kg LD (Dose 1) followed by nine 40 mg/kg MDs (Doses 2 to 10) of lumicitabine, administered twice daily.
- Regimen C (placebo): those randomized to a placebo regimen are subsequently randomized in a 1:1 ratio (to match volumes) to either:
 - A single 40 mg/kg placebo LD (Dose 1) followed by nine 20 mg/kg MDs (Doses 2 to 10), administered twice daily.
 - A single 60 mg/kg placebo LD (Dose 1) followed by nine 40 mg/kg placebo MDs (Doses 2 to 10), administered twice daily.

An IDMC (refer to Section 3.2, Independent Data Monitoring Committee, for details) will review the safety and PK data once the first 12 subjects and 30 subjects have completed treatment (Day 5/6) to assess if enrollment of additional subjects may safely continue in each arm. After at least 9 subjects have completed treatment with the 60 mg/kg LD/40 mg/kg MD lumicitabine regimen, the IDMC may recommend that sparse PK sampling be used for the other subjects. Subject recruitment and enrollment may continue while the data are being reviewed.

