Up to 2 formal interim analyses may be performed during the study. The first interim analysis will be performed once 36 subjects with ≤ 3 days of RSV symptoms have completed treatment (Day 5/6) or once 90 subjects with >3 to ≤ 5 days of RSV symptoms have been enrolled and have completed treatment. The following situations will be considered based on the results at this stage: that the study is considered futile; that superiority can be concluded; that subjects with >3 to ≤ 5 days of RSV symptoms at randomization may not achieve benefit (which may also be limited to ≤ 4 days of onset to symptoms); or that the study can continue unchanged. The treatment regimen may be modified after the first interim analysis, including increasing the treatment duration up to 10 days. After this analysis, randomization to 1 of the lumicitabine doses may be discontinued, the randomization ratio may change, and the study may not continue in subjects with >3 to ≤ 5 days of RSV symptoms at randomization. The second interim analysis may be performed at the discretion of the sponsor once at least 120 subjects have completed treatment (Day 5/6) (or at least 60 subjects with ≤ 3 days of RSV symptoms). The following situations will be considered based on the results at this stage: that the study is considered futile; that superiority can be concluded; or that the study can continue unchanged. Based on the recommendations of the IDMC following these interim analyses/reviews of PK, efficacy, and safety data, changes to randomization ratios in the treatment arms or an increase in treatment duration to 10 days may be implemented.

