1.4. Sample Size Justification

On high dose, the hypothesis of the lumicitabine antiviral activity assumes a viral load reduction on the AUC of the log viral load over 7 days of at least 30% when compared to placebo in subjects with onset of symptoms ≤ 3 days and of at least 20% in subjects with onset of symptoms > 3 days. The antiviral activity on low dose is assumed to be 80% when compared to the antiviral activity on the high dose. The positive dose-response relationship assumes that dose regimens with higher exposure with respect to MD will have at least an equal or better effect on viral load. Therefore 2 contrasts will be tested at each of the interim analysis points and final analysis; a contrast with no difference between the 2 active regimens tested against placebo (high equal to low, better than placebo) and a contrast with a positive ‘linear’ dose-response relationship (high better than low, low better than placebo) with respect to active regimens (where the effect of the low dose is exactly in between that of placebo and the high dose regimen). With respect to multiple contrast testing, multiplicity (2 contrasts) will be controlled at the prespecified (interim) alpha level by calculating adjusted p-values from the simulated distribution of the maximum or maximum absolute value of a multivariate t random vector (ie, using the correlation between the contrasts to optimally control for alpha).

Based on the observed data of other in-house studies, the estimated SD is assumed to be approximately 34% of the AUC for subjects treated with placebo and the SD is equal in each of the treatment regimens. The overall (family wise) type 1 error rate of 2.5% (1-sided) will be adjusted for multiple testing due to formal interim analyses using a Pocock alpha spending function with 3 sequential tests (2 interim, 1 final). Based on 10,000 simulations and using a general linear model with treatment regimen as fixed factors, and under the assumption that 40% of the recruited subjects have onset of symptoms ≤ 3 days, a sample size of 180 subjects randomized in a 1:1:1 ratio will offer approximately 97% power to detect a positive dose-response relationship using multiple contrast testing. With the second interim analysis planned after at least 120 subjects, there will be at least 80% power to detect a positive dose-response relationship at the time of this analysis.

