5.1. Analysis Specifications

5.1.1. Level of Significance

Two contrasts will be tested at each of the interim analysis points and final analysis; a contrast with no difference between the 2 active regimens tested against placebo (high equal to low, better than placebo) and a contrast with a positive ‘linear’ dose-response relationship (high better than low, low better than placebo) with respect to active regimens (where the effect of the low dose is exactly in between that of placebo and the high dose regimen). With respect to multiple contrast testing, multiplicity (2 contrasts) will be controlled at the prespecified (interim) alpha level by calculating adjusted p-values from the simulated distribution of the maximum or maximum absolute value of a multivariate t random vector (ie, using the correlation between the contrasts to optimally control for alpha).

The significance level of *alpha* (α^*) will have to be calculated based on the information fraction at the time of the test using the pre-specified Pocock α spending function.

$$\alpha^*(t) = \alpha \cdot \ln(1 + (e-1) \cdot t)$$

where $t = n/N$, n is the ITT-i set size and N is the expected ITT-i set size at the end of study (=120).

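### SAP 5.1.1 puts N = 120 in the alpha-spending function of a trial planned for up to 180 subjects and powered on 180, so testing beyond about 120 either overspends the 2.5% or has almost no alpha left

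*SAP*

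**What the plan says.** SAP 5.1.1 (Level of Significance) says that the level at each test is "calculated based on the information fraction at the time of the test using the pre-specified Pocock α spending function". It gives the function as `0.025 × ln(1 + (e − 1)t)` in effect, with t = n/N. Here n is the current ITT-i size and N "is the expected ITT-i set size at the end of study (=120". It does not say what happens when t reaches or passes 1.

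Other parts of the SAP describe a larger trial:

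- Section 1.2.1 (Option A) plans 60 subjects per regimen: "At least 120 subjects are planned to be enrolled up to a maximum of 180 subjects".
- Section 1.4 (Sample Size Justification) says that "a sample size of 180 subjects randomized in a 1:1:1 ratio will offer approximately 97% power", and that error is controlled "using a Pocock alpha spending function with 3 sequential tests (2 interim, 1 final".
- Sections 1.2.1 and 3.1 treat 120 as the minimum for an interim: "The second interim analysis may be performed at the discretion of the sponsor once at least 120 subjects have completed treatment". An alternative trigger is 60 subjects with early symptom onset.

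The protocol (3.1.1, 11.2, 11.9) has the same 120 to 180 range and the same three tests. It does not state N = 120. Nothing in either document reconciles 120 with 180.

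**The concern.** One number, 120, is the end-of-study size in the spending rule and also the earliest size for the second of two interims. A spending function allots the full error rate at t = 1. If t = 1 falls at the second interim, the planned final test has no legitimate share.

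This rule decides whether the primary hypothesis is declared met. SAP 3.1 lets a crossed superiority boundary support early termination and lets interim results go to health authorities. If N is left to be settled after unblinded data have been seen, the threshold is no longer prespecified.

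**Working it through.** **1. The plan's own power.** Inputs from SAP 1.4: high-dose reduction 30% (onset ≤3 days) and 20% (>3 days), 40% early onset, low dose at 80% of the high-dose effect, SD 34% of placebo AUC, 1:1:1 allocation, one-sided 0.025.

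- Average effects: high = 0.4 × 30 + 0.6 × 20 = 24%; low = 0.8 × 24 = 19.2%; mean of the two = 21.6%.
- Contrasts (−1, ½, ½) and (−1, 0, 1), with correlation 1.5/√(1.5 × 2) = 0.866.
- Expected z at 60 per arm: 21.6/(34 × √(1.5/60)) = 4.02 and 24/(34 × √(2/60)) = 3.87.

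The first look is placed at n = 90. This is an assumption: 36 early-onset subjects divided by 0.40. Simulation with N = 180 and looks at 90, 120 and 180 gives cumulative power of 84 to 86% by 120 and 96 to 97% by 180, depending on the run. The stated figures (at least 80%, about 97%) are therefore consistent with N = 180.

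**2. Cumulative alpha from the 5.1.1 formula.**

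| n | t (N = 120) | spent | t (N = 180) | spent |
|---|---|---|---|---|
| 90 | 0.75 | 0.0207 | 0.50 | 0.0155 |
| 120 | 1.00 | 0.0250 | 0.67 | 0.0191 |
| 150 | 1.25 | 0.0287 | 0.83 | 0.0222 |
| 180 | 1.50 | 0.0319 | 1.00 | 0.0250 |

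For example, at t = 1.5: 0.025 × ln(1 + 1.71828 × 1.5) = 0.025 × ln(3.5774) = 0.0319. Cumulative spend depends only on t at the last test, so these end values do not rest on the assumed look at 90.

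**3. Continuing past 120 with N = 120.**

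- No cap: with boundaries derived from the increments, family-wise error at n = 180 is 3.19% against 2.5%.
- Capped at t = 1, look taken at 120: remaining alpha is 0.0250 − 0.0250 = 0.
- Capped, second look at 114 ITT-i subjects (an illustrative count): t = 0.95, 0.0242 is spent and 0.0008 is left. The final nominal level on the multiplicity-adjusted p-value is about 0.0027.
- Capped, second interim skipped: 0.0250 − 0.0207 = 0.0043 is left, against 0.0250 − 0.0155 = 0.0095 with N = 180.

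**4. Stopping at 120 with N = 120.** Expected z values fall to 4.02 × √(120/180) = 3.28 and 3.87 × √(120/180) = 3.16. With looks at 90 and 120, error stays at 2.5% and power is about 88%. With no earlier look it is about 91%.

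**The case against.** The strongest defence is that 120 lies within the planned range and that 5.1.1 speaks of an expected size, not a maximum. The SAP was written after Option A had been chosen, so 120 may be a deliberate forecast. This stands as far as it goes: if the trial ends at 120 ITT-i subjects, the error rate is not exceeded. It does not explain why the same SAP still describes 180 subjects and a further test after 120.

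A reader might infer several stronger claims that the documents do not support:

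- **That the 2.5% limit will be broken.** This needs more than 120 ITT-i subjects, a further test, and the formula applied beyond t = 1. Section 1.4 does state the overall 2.5% limit, so a statistician could reasonably cap t. The harm is then lost alpha, not excess error.
- **That the second interim cannot exist.** It is optional, and the trigger of 60 early-onset subjects can fall below 120 ITT-i subjects.
- **That the SAP misstates its power if the trial stops at 120.** The 97% is stated for 180. For 120 the SAP claims at least 80%, and 88% satisfies that.
- **That the error rate is about 5.1%.** That figure arises if the cumulative value is also used as the nominal level at each look, which is a separate problem. It gives 4.0% even with N = 180.

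The Interim Analysis Plan is not available and may set boundaries. However, SAP 5.1.1 itself states N and covers the final analysis. Skipping the second interim does not help either: a final test at 180 still has t = 1.5.

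**Conclusion.** The rule is wrong as written for the planned design and should be corrected before the first unblinded analysis. The inconsistency between N = 120 and the 180-subject, three-test plan is certain from the text. Its consequence depends on the branch:

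- **Beyond 120 ITT-i subjects, no cap:** cumulative spend is 2.87% at 150 and 3.19% at 180.
- **Beyond 120, t capped at 1:** error is held at 2.5%, but little or nothing remains for the final test.
- **Final size 120:** no type 1 excess. Power is about 88%, and the 180-subject, three-test, 97% statement does not describe the trial.

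The spending figures follow from the formula alone. The power figures rest on the SAP 1.4 assumptions, on treating enrolled and ITT-i counts as equal and, for the 88%, on looks at 90 and 120.

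**What to change.** In SAP 5.1.1, and consistently in the Interim Analysis Plan:

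1. Set N to the planned final ITT-i size on which the power rests: 180, or 180 less the expected ITT-i exclusions.
2. State that the formula gives cumulative alpha and that each look uses the boundary for its increment. With N = 180 and looks at 90, 120 and 180, cumulative spend is 0.0155, 0.0191 and 0.0250. The nominal levels on the adjusted p-value are about 0.0155, 0.0091 and 0.0109. Changing N without this statement is not enough.
3. State that the final analysis uses t = 1 and spends only the remaining alpha, whatever the final n. Without this, a trial ending at 150 with N = 180 would use only 0.0222.

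Power then stays at about 97% for 180 subjects.

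Alternatively, if 120 is the decided final size, keep N = 120, state that any look at 120 is the final test, and restate the power in section 1.4 as about 88%.

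Either route costs a few lines of text and needs no new data, provided that it is done before unblinded results are seen.

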5.1.2. Data Handling Rules

For analysis purposes the \log_{10} qRT-PCR viral load will be imputed with 0 when the result is ‘negative’, and the midpoint on the \log_{10} scale between the limit of detection and limit of quantification when the result is ‘positive’ but non-quantifiable. For the qRT-PCR assay used for detection and quantification of RSV-A and RSV-B, the lower limit of quantification (LLOQ) is 3 \log_{10} (copies/mL) for RSV-A and 2.4 \log_{10} (copies/mL) for RSV-B, the limit of detection (LOD) is 2.7 \log_{10} (copies/mL) for RSV-A and 1.9 \log_{10} (copies/mL) for RSV-B.

5.2. Primary Efficacy Endpoint(s)

5.2.1. Definition

RSV RNA will be measured in mid-turbinate nasal swab specimens using an RSV-A/B qRT-PCR developed by DDL Diagnostic Laboratory.

The primary endpoint is RSV RNA \log_{10} viral load (measured by qRT-PCR in the mid-turbinate nasal swab specimens) area under the concentration-time curve (AUC) from immediately prior to first dose of study drug (baseline) until Day 7.

The primary estimates of the $AUC_{1-7 \text{ Days}}$ will be derived from a mixed model (see section 5.2.3 for the detailed specification). No imputations of missing data from nasal swabs post-baseline will be done in this model, as this mixed model would allow to make inferences under the missing at random assumption.

Note that for the primary endpoint the following rules apply:

- Only values as provided by the central lab will be used.
- Baseline is defined as the last measurement before first intake. In case a result is available that is no later than 1 hour after treatment initiation this may be used but only if no pre-treatment observation is available.
- For all post-baseline analysis visits the RSV RNA log₁₀ viral load result of the swab that was performed at that day will be used.
- In case multiple nasal swabs were taken on a single day the maximum on the log scale will be used as the value for that subject.

As a sensitivity analysis, descriptive statistics will be provided for the viral load AUC between 0h and 144h (AUC_{0-144h}); calculated by the trapezoidal summation rule, based on date time of sampling, including the timepoints with (imputed) values available:

$$AUC_{0-144h} = \frac{1}{2} \sum_{i=1}^n (y_i + y_{i-1}) \times (t_i - t_{i-1})$$

where $i=1,2,3,\dots,n$ are the time points when post baseline samples are collected, y_i is the log 10 viral load at the time and t_i is the time in hours post baseline. y_0 is the (imputed) log 10 viral load at baseline, t_0 is time 0 and t_n is time 144h.

The following additional rules, on top of the rules of the primary analysis, will be applied to deal with missing values before calculating the Viral load AUC_{0-144h}:

- The value at time point 0h, if not exactly at 0h, will be calculated based on intrapolation between the last observed pre-dose value and the first observed post-dose value.
- The value at 144h, if not exactly at 144h, will be calculated based on intrapolation between the last observed value before 144h and the first observed value after 144h.
- Missing values between 0h and 144h will be imputed by intrapolation.
- If the last observation is missing, the last available observation will be carried forward until 144h is reached.

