The *lower* option is selected as the contrast needs to have a value below zero (ie, there needs to be a reduction in $AUC_{1-7\text{Days}}$ comparing active treatment to placebo). In summary, a positive dose-response relationship will be concluded if based on this analysis for any of the two estimations the resulting adjusted p-value is lower than the associated Pocock critical value (see section 5.1.1).

The differences in the $AUC_{1-7\text{Days}}$ for active versus placebo will be derived using appropriate contrasts deriving least square mean differences, including the 95% 2-sided confidence intervals.

The individual $AUC_{0-144\text{h}}$ as calculated using the trapezoidal rule will be considered as a supportive analysis and will be analyzed using a linear model with $AUC_{0-144\text{h}}$ as a dependent variable and treatment group and stratum as fixed factors, and baseline \log_{10} viral load as fixed covariate. For this analysis no adjustments for multiplicity will be applied, that is the differences versus placebo will be estimated using appropriate contrasts with 95% confidence intervals.

Before unblinding, the viral load data will be evaluated to assess whether viral load measurements based on swabs performed by the Health Care Provider (HCP) are similar as the swabs not performed by a HCP. Individual line plots will be created to visually check individual patterns for any difference between the samples. Depending on the visual inspection a decision will be made if all samples or only the samples from swabs performed by a HCP will be considered for the primary analysis. For example, if for the majority of subjects there is a clear drop in viral load when switched from samples taken by a HCP and samples taken by a non-HCP, the decision could be that only samples from swabs done by a HCP will be used. This blinded data review will be done before the database lock of the interim analysis and may also take other data sources into account.

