5.3.1.1. RSV RNA \log_{10} viral load (qRT-PCR)

Table 1: Calculations and Conversion Formulae

Measurement	Formula
\log_{10} viral load actual values	\log_{10} of the actual values as measured with qRT PCR
\log_{10} viral load	Change = \log_{10} viral load actual value – \log_{10} baseline value

change from baseline	
Peak viral load	Highest value of \log_{10} viral load at or after the baseline measurement. The first record in time with this highest value is selected. This can be the baseline record or an unscheduled record.
Rate of decline of viral load over the first 24 hours	Calculated as a log decline/24 hours defined as: (24-hour log viral load after first dose of study drug – log viral load at baseline) / (date/time of 24-hour viral load sample – date/time of baseline viral load) Note, the 24-hour viral load may not have been measured at exactly 24 hours following first dose, but the actual date/time associated with the 24-hour viral load will be used in computing the viral load slope. In case the 24 hour measurement is not available the slope will be calculated using the Day 3 assessment (48 hours), using the same definition. If there is no measurement in that time frame, the slope will not be calculated.
RSV viral load AUC_{0-240h} RSV viral load AUC_{0-336h} [trapezoidal method]	Idem as RSV viral load AUC_{0-144h} from 0 hours until 144 hours using the trapezoid method (sensitivity analysis), but from 0 hours until 240 hours and 336 hours respectively.
RSV viral load AUC_{0-xxh} [trapezoidal method]	Idem as RSV viral load AUC_{0-144h} using the trapezoid method, but from 0 hours until xx hours, where xx will be calculated as 24 times the number of days with treatment + 1 day.
Time to peak viral load (hours) [Time-to event]	The time from initiation of study treatment until the first time point with the peak viral load (= event). Subjects for which the peak was reached at the baseline measurement will have time 0. Subjects for whom the peak is reached at the last observed time point will be censored at that time point. Subjects for which this last assessment is the baseline assessment will be censored at time 0. (Date and time of event or censoring - date and time of first dose of study drug)/3600, rounded to one decimal.

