5.3.2.1. RSV RNA \log_{10} viral load qRT-PCR

Log₁₀ Viral Load

Descriptive statistics and mean (SE) graphs will be shown of the \log_{10} viral load actual values and changes from baseline. For exploratory purpose the \log_{10} viral load actual values and changes from baseline will also be shown by sampling method (measured in the mid-turbinate nasal swabs and endotracheal samples from intubated subjects).

Differences on RSV RNA \log_{10} viral load by qRT PCR between treatment groups and by analysis visit will be determined by using appropriate contrasts in the mixed model in which the primary endpoint is modelled. Nominal 95% confidence intervals will be used.

Peak viral load; Rate of decline

The Rate of decline of viral load over the first 24 hours will be analyzed using descriptive statistics including the geometric mean and the coefficient of variation (CV).

The log peak viral load and rate of decline of RSV RNA viral load will be compared for active groups versus placebo groups using a general linear model with treatment and strata included as fixed effects.

Residuals of the final model will be plotted in a normal probability plot.

In case the model does not fit the log peak value data well, the log transformation (ie. the log of log peak viral load) will be considered as dependent variable. The data from the model will be reported as (adjusted) differences in least squares (LS) means (in the case of untransformed data) or (adjusted) geometric mean ratios (in case of log-transformed data) of active dose groups versus placebo, including 95% confidence intervals using appropriate contrasts.

RSV viral load AUC's.

The same model used for the primary analysis will be used to test for a dose response relationship on the viral load AUC until Day 10, until Day 14 and until 1 day after last dose for subjects with treatment extension (if applicable) (respectively $AUC_{1-10Days}$, $AUC_{1-14Days}$ and $AUC_{1-xxDays}$). No corrections for multiplicity will be made, thus the significance level of alpha (α^*) will be kept at 0.05. The differences in these AUCs for active versus placebo will be derived using appropriate contrasts deriving least square mean differences, including the 95% 2 sided confidence intervals.

The sensitivity analysis will be similar as for the primary endpoint, using the calculated viral load AUCs per subject based on the trapezoidal method (AUC_{0-240h} , AUC_{0-336h} and AUC_{0-xxh}) as indicated in section 5.3.1.1.

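### The supportive trapezoidal viral-load AUCs (to 144, 240 and 336 h) carry the last swab forward without a rationale, which overstates AUC when viral load is falling and can distort the treatment difference in either direction

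*SAP*

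**What the plan says.** The primary AUC over Days 1 to 7 comes from a repeated-measures model with no imputation of post-baseline swabs. SAP 5.2.1 justifies this because "this mixed model would allow to make inferences under the missing at random assumption".

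The same section defines a second, per-child AUC0-144h by the trapezoidal rule on actual sampling times. Its rules for missing swabs are:

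- Gaps: "Missing values between 0h and 144h will be imputed by intrapolation".
- The end value, if a later swab exists, "will be calculated based on intrapolation between the last observed value before 144h and the first observed value after 144h".
- The end value, if no later swab exists: "If the last observation is missing, the last available observation will be carried forward until 144h is reached".

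SAP 5.3.1.1 defines the longer AUCs as the same quantity, "but from 0 hours until 240 hours and 336 hours respectively", and treats the extended-dosing AUC likewise. SAP 5.2.3 states that the 144 h AUC "will be considered as a supportive analysis and will be analyzed using a linear model", with treatment, stratum and baseline as terms. It adds: "For this analysis no adjustments for multiplicity will be applied". SAP 5.3.2.1 says of the longer windows: "The sensitivity analysis will be similar as for the primary endpoint". SAP 5.3.2.3 also cuts AUC0-144h into quartiles, to be related to oxygen use, hospital stay, clinical stability and symptom severity.

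**The concern.** RSV is an acute infection, and the plan's hypothesis is that viral load falls faster on drug. Holding a child's value flat after the last swab therefore overstates that child's AUC, and by more in the arm where load falls faster. The longer the window beyond the last swab, the larger the error.

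Three uses are affected: the supportive treatment estimates and their confidence intervals, which treat carried values as observed; the same estimates at 240 h and 336 h; and the quartile analyses, where early loss pushes a child towards a higher quartile. The supportive analysis also changes the AUC method and the missing-data assumption together. If it disagreed with the primary result, the reader could not tell which change was responsible.

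**Working it through.** **1. The plan's own figures.** From SAP 1.4: high-dose reduction 30% (onset ≤3 days) and 20% (>3 days), 40% of children with early onset, SD 34% of placebo AUC, 180 children 1:1:1, Pocock spending.

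- Average high-dose effect: 0.4 × 30% + 0.6 × 20% = 24%. Low dose: 0.8 × 24% = 19.2%.
- Simulating the larger of the plateau and linear contrasts, with looks at 90, 120 and 180 and information fraction n/180 (SAP 5.1.1 divides by 120, a separate matter), gives 96.7% power at 180 and 85.9% cumulative at 120.

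The stated 97% and at least 80% reproduce. Neither uses the carried-forward AUC.

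**2. Overstatement for one child.** The documents give no trajectory, so assume a linear log10 decline floored at 0, baseline 5 to 7 and slope 0.2 to 0.8 per day. Inflation of the child's AUC:

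| Last swab | 144 h | 240 h | 336 h |
|---|---|---|---|
| 24 h | 7–64% | 14–171% | 22–279% |
| 72 h | 2–23% | 8–89% | 15–156% |
| 120 h | 0–3% | 4–31% | 10–70% |

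**3. Effect on the 144 h difference.** Assume baseline 6.5 and placebo slope 0.45 per day.

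- Placebo AUC over 6 days: 6 × 6.5 − 0.45 × 18 = 30.9 log10-days.
- Active AUC: 0.76 × 30.9 = 23.484, so the active slope is (39 − 23.484)/18 = 0.862 per day.
- True difference: 30.9 − 23.484 = 7.416.
- With last swab d days after baseline (Day 1 is d = 0), carrying forward adds slope × (6 − d)²/2 to a child's AUC.
- The share of the difference kept among affected children is 1 − (6 − d)²/36.

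For 10% of children affected:

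| Last swab | Share kept | Equal loss | Active only | Placebo only |
|---|---|---|---|---|
| Day 1 | 0% | −10% | −21% | +11% |
| Day 2 | 31% | −7% | −15% | +8% |
| Day 3 | 56% | −4% | −9% | +5% |
| Day 4 | 75% | −2.5% | −5% | +3% |

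For example, Day 1 with loss on active only is 0.1 × 0.862 × 18 / 7.416 = 21%.

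**4. When does the sign turn?** For the same last-swab day, the change is proportional to (active loss × 0.862) − (placebo loss × 0.45). Inflation needs placebo loss above 0.862/0.45 = 1.9 times active loss.

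**5. 336 h (14 days), same trajectory.**

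- Placebo: 91 − 0.45 × 98 = 46.9.
- Active reaches 0 at 6.5/0.862 = 7.54 days: 6.5 × 7.54/2 = 24.5. Difference: 22.4.
- Active child last swabbed on Day 1: carried AUC 91, excess 66.5. At 10% on active only, 6.65/22.4 = 30%.
- Active child last swabbed on Day 5: value 6.5 − 4 × 0.862 = 3.05; carried AUC 4 × (6.5 + 3.05)/2 + 10 × 3.05 = 49.6, excess 25.1. At 10% on active only, 2.51/22.4 = 11%.

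**6. Second trajectory** (baseline 6.5, placebo slope 0.4, active 0.824, last swab at 24 h):

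| Loss, placebo / active | 144 h | 240 h | 336 h |
|---|---|---|---|
| 5% / 15% | −17.0% | −20.2% | −24.6% |
| 15% / 5% | +3.1% | +4.4% | +9.0% |

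With no drug effect, equal loss gives no bias. Loss of 15% against 5% gives a spurious difference of 1.6%, 3.6% and 6.5% of placebo AUC at the three windows.

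**7. Loss spread over time.** In a simulation of dropout under missing at random, with about 9% of placebo and 20% of active lost by Day 7, carry-forward gave −7.29 against a true −7.65 (5% attenuation). With about 20% and 38% lost it gave −6.87 against −7.66 (10%). A likelihood estimate under missing at random recovered the true value both times.

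**The case against.** The strongest reply is that this is a secondary matter, working as intended. Missing at random is claimed only for the primary model, and a sensitivity analysis may use another assumption. A reader might infer that the SAP contradicts itself or that the primary conclusion is at risk. Neither follows: the trapezoidal AUC is separate, carries no multiplicity control and does not decide the dose-response test. Nor does it betray an AUC difference promised in the objective. The objective names a dose-response relationship on shedding; the AUC difference appears in SAP 5.2.2 and comes from the mixed model.

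The trigger is also narrow. A child who misses home swabs but returns for any later swab is interpolated, and Protocol 10.2 encourages follow-up after stopping drug. Inclusion criterion 2 requires children unlikely to be discharged within 24 hours, so a last swab on Day 1 should be uncommon. A reader might infer that a baseline-only child gets baseline times 144 h. That is a literal reading of the rule, but the SAP does not state the case.

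The 144 h shift is modest. A 5% or 10% attenuation of a 24-point effect is 1.2 or 2.4 points of placebo AUC. The unadjusted standard error of a pairwise difference is 34 × √(2/60) = 6.2 points, so the shift is about 0.2 to 0.4 standard errors.

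All of this stands, and it limits the point. It does not supply a reason for the rule. A sensitivity analysis should probe a plausible departure, and a frozen viral load in a resolving infection is not one. A gap between the two analyses could also come from sampling times versus visit windows, which makes it harder still to interpret.

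**Conclusion.** The carry-forward rule should be replaced. It is an unexplained and implausible assumption for falling viral load. It overstates AUC for children with no later swab, and it reaches the 240 h and 336 h windows and the outcome quartiles. On the assumed trajectories the distortion at 144 h is from a few percent to about a fifth of the treatment difference per 10% of children affected. At 336 h it is 11% to 30% if loss is confined to active.

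A reader might infer that the bias always works against the drug. It does not: equal or active-heavy loss attenuates the difference, while placebo loss above roughly twice active loss inflates it. All sizes rest on assumed baselines, linear slopes and dropout, because the documents give neither a dropout rate nor a trajectory. The primary test and its stated power do not change.

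**What to change.** In SAP 5.2.1 and 5.3.1.1, before unblinding:

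- Replace the carry-forward bullet with multiple imputation of missing tails from the primary repeated-measures model. For 240 h and 336 h add Days 10 and 14, and the next scheduled swab where needed.
- Keep interpolation between observed swabs. Compute the trapezoidal AUC and fit the supportive model in each completed data set, and combine by Rubin's rules.
- Add a stated delta shift to the imputed values. Without it, the analysis would largely repeat the primary result.
- For the AUC0-144h quartile and correlation analyses in SAP 5.3.2.3, use each child's mean over imputations, or restrict to children whose AUC needs no imputed tail.
- Report the number of children with imputed tails by arm and window. If carry-forward is kept, label it as an additional analysis only.

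The cost is SAP wording and modest extra programming. The per-child AUC is no longer a single derived value for children with missing tails.
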